1	09/10/2012	Replace 1-MT with newer name of indoximod throughout protocol including title; Add affiliate names and contact information; Update research related lab instruction; increase blood volume from 60 ml to 90 ml; add a 2 nd baseline collection, move week 8 time point to week 10 to match schema; Section 8.3 – add SAE reporting to Dendreon and NewLink; minor edits throughout	09/10/2012
2	10/15/2012	Update dose of indoximod to 2400 mg in a divided dose twice a day as it represents the current phase II dosing (the dose currently being used in clinical trials) – increase # of placebo capsules to match the new dose; Section 3.7 and appendix I - Relax baseline serum creatinine to < 2.0 mg/dL to align with other similar trials and lack of renal toxicity in either drug.	10/15/2012
3	07/15/2013	Schema and section 4.2 - Change randomization from at time of enrollment to week 4 Schema and section 6.2 - Add to SOC - serum collection for circulating tumor cells (CTCs) at baseline and week 14 Schema and section 6 - Permit 2 nd baseline research blood sample to be drawn at any time prior to the first sipuleucel-T infusion Schema and section 6.2 - Separate research related serum collection (all patients) and tumor biopsy at pre and at week 14 (optional requiring additional consent) Section 5.2.2 – clarify positive ANA must be > 5 times upper limit of normal before additional testing/treatment modification is required Title page and Key Contact Info - Update affiliates sites and investigators Other minor updates throughout protocol	no changes

Revision #	Version Date	Details of changes	Consent change?
4	09/02/2014	
Title page and Key Contact Info – update affiliate sites and investigators
 
Section 3.7 and appendix I – delete ANC eligibility requirement, add CD4 count > 400 eligibility requirement if WBC <= 3,000
 
Section 8.4 table - Update telephone number for Dendreon Corporation Serious Adverse Event reporting
 
Update table of contents to show 2 levels of headings
 
Other minor edits as tracked
	minor updates

9.1	Immune Response to PA2024.....	34
9.2	Progression Free Survival	34
9.3	PSA Progression	35
9.4	Imaging Progression.....	35
10	Study Data Collection and Monitoring.....	35
10.1	Data Management	35
10.2	Case Report Forms	35
10.3	Data and Safety Monitoring Plan (DSMP).....	36
10.4	Monitoring.....	36
10.5	Record Retention.....	37
11	Study Endpoints.....	37
11.1	Primary Endpoint	37
11.2	Secondary Endpoints.....	37
12	Statistical Considerations.....	37
12.1	Power and Sample Size	38
12.2	Early Termination for Excess Toxicity.....	38
13	References.....	39
	Appendix I – Eligibility Checklist.....	40
	Appendix II - Performance Status Scales	42
	Appendix III – RECIST v 1.1	43
	Appendix IV - Auto-Immune Symptom Evaluation Checklist	47
	Appendix V – FACT P (version 4).....	48

Protocol Synopsis

A Randomized, Double-Blind Phase II Study of Sipuleucel-T (Provenge®) Followed by Indoximod or Placebo in the Treatment of Patients with Asymptomatic or Minimally Symptomatic Metastatic Castration Resistant Prostate Cancer

Study Design: This is a randomized, double blind, multi-institutional phase II therapeutic study of indoximod or placebo after the completion of standard of care sipuleucel-T (Provenge®) in men with asymptomatic or minimally symptomatic metastatic prostate cancer that is castration resistant (hormone refractory). Patients are randomized to receive either twice daily oral indoximod or placebo for 6 months beginning the day after the third and final sipuleucel-T infusion.

Research related correlatives will include serial blood sampling for immune monitoring and an optional prostate or metastatic site biopsy at enrollment and at week 14.

Primary Objective: To assess the augmentation of immune response to sipuleucel-T measured at 14 weeks from first leukapheresis, in response to twice daily oral indoximod at a dose of 2400 mg/day or an identical looking placebo

Secondary Objectives:

- To assess the safety of indoximod when administered post sipuleucel-T therapy
- To assess efficacy as measured by improvement in time to disease progression, objective response rate, overall survival
- To assess health related quality of life improvement on therapy

Inclusion Criteria:

- Metastatic castration resistant prostate cancer
- Serum PSA \geq 2.0 ng/ml at study enrollment
- Planned standard of care treatment with sipuleucel-T
- Asymptomatic or minimally symptomatic disease as demonstrated by ECOG Performance Status 0 or 1 and no need for opiate pain medications to control pain/symptoms
- Adequate organ function within 14 days of study enrollment

Study Population: Men with asymptomatic or minimally symptomatic castration resistant prostatic adenocarcinoma

Sample Size: Approximately 50 subjects will be enrolled (1:1 indoximod vs placebo) at up to 5 sites

Duration of Treatment: Sipuleucel-T will be administered as standard of care either at the study center or by the referring physician. Oral indoximod /placebo will be self-administered twice daily for 6 months starting after the last infusion of sipuleucel-T. Patients will be treated for a minimum of 12 weeks of indoximod /placebo before disease progression can be declared and indoximod /placebo will not be discontinued for increasing PSA in the absence of symptomatic clinical progression.

Schema

Enrollment Plan:

Eligible, consenting patients will be enrolled to the study prior to the first leukapheresis (week 0). Randomization to either indoximod or placebo will occur at the beginning of week 4 (the week of the 3rd leukapheresis/sipuleucel-T infusion).

Treatment Plan:

Sipuleucel-T (Provenge®) - leukapheresis at weeks 0, 2, and 4 with sipuleucel-T infused 3 days later per Standard of Care

Indoximod 2400 mg/day or Placebo – begin 1 day after last sipuleucel-T infusion, continue twice daily for 6 months (24 weeks)

Immune Monitoring/Indoximod Levels:

1. At the time of screening/consent signature (1st baseline sample)
2. Any time prior to the first sipuleucel-T infusion on week 0 (2nd baseline sample)
3. After 3rd sipuleucel-T infusion on week 4
4. 2 weeks from initiation of treatment with indoximod/placebo on week 6
5. 6 weeks from initiation of treatment with indoximod/placebo on week 10
6. 10 weeks from initiation of treatment with indoximod/placebo on week 14
7. 24 weeks from initiation of treatment with indoximod/placebo on week 28

Immune Response Biomarkers - Serum Sample:

1. Any time prior to the first sipuleucel-T infusion on week 0
2. 10 weeks from initiation of treatment with indoximod/placebo on week 14

Biopsy (optional):

1. Prior to first leukapheresis on week 0
2. 10 weeks from initiation of treatment with indoximod/placebo on week 14

1 Objectives

1.1 Primary Objective

The primary objective of this study is to assess the augmentation of immune response to sipuleucel-T measured at 14 weeks from first leukapheresis, in response to twice daily oral indoximod at dose of 2400 mg/day or an identical looking placebo.

1.2 Secondary Objectives

- To assess the safety of indoximod when administered post sipuleucel-T therapy
- To assess efficacy as measured by improvement in time to disease progression, objective response rate, overall survival
- To assess health related quality of life improvement on therapy

1.3 Correlative Objectives

- To assess immune response at subsequent time points through week 28 and validate detection of PA2024 antibody response
- To assess other immune monitoring data including immunophenotyping

2 Background and Rationale

2.1 Prostate Cancer

Prostate cancer is the most common solid tumor malignancy in men in the United States. It is estimated that 217,730 men will be diagnosed with and 32,050 men will die of cancer of the prostate in 2010.(1)The vast majority of men are diagnosed at a localized stage and treated with prostatectomy or radiation therapy. While the overall five-year relative prostate cancer survival rate for 2001-2007 was 99.4 percent(1); approximately 1 in 3 men with early stage prostate cancer will experience a rise in the PSA levels within 5 years after initial treatment. At this point androgen ablation either through surgical or medical castration is the standard treatment for metastatic or recurrent disease. However this is only a temporary fix as most men who survive long enough (as the median age of diagnosis is 67 years) eventually develop castration resistant disease. The offer of chemotherapy with docetaxel suggests a survival benefit, but due to the associated “quality of life” side effects (alopecia, fatigue, neutropenia, and neuropathy) most men with asymptomatic disease will delay treatment until symptomatic. Thus, alternate treatment options are needed for this group of men with metastatic castration

resistant prostate cancer who, despite their disease maintain a good performance status with little or no disease associated symptoms.

2.2 Sipuleucel-T (Provenge)

After decades of promise and research, sipuleucel-T (Provenge) has been the first vaccine therapy approved for treatment of any cancer in the United States. Sipuleucel-T involves *ex-vivo* sensitization of peripheral blood mononuclear cells to a custom prostatic acid phosphatase and granulocyte monocyte – colony stimulating factor (GM-CSF) fusion protein (PA 2024) followed by autologous transfusion. Sipuleucel-T is very well tolerated with mostly grade 2 side effects consistent with cytokine release. It has shown to improve survival by 3-4 months as compared to placebo in randomized, double blinded phase III clinical trials.(2, 3) Besides this modest improvement in survival, there has been no improvement in time to objective disease progression or an objective response rate (>25% decline in PSA).(2, 3) Although this has been a huge first stride in development of immunotherapies and first proof of principle, additional progress needs to be made before this technology has its fullest and most widely-applicable impact in treating cancers of prostate and other malignancies.

2.3 1-methyl-D-tryptophan (1-MT, indoximod)

Indoleamine 2,3-dioxygenase (IDO) is a key immune-modulatory enzyme that degrades tryptophan to bioactive kynurenine metabolites. The process and effects of tryptophan depletion and kynurenine metabolism together form the immuno-modulatory IDO pathway(4), which promotes peripheral immune tolerance by direct inhibition of effector T cells, activation of pre-existing Foxp3+ Tregs, and conversion of naïve T cells to Tregs. 1-MT is a competitive inhibitor of the immunoregulatory enzyme, IDO, a critical regulator of immunosuppressive responses.

In the preclinical studies, 1-MT was readily absorbed following oral administration in mice, rats, and dogs and the bio-availability ranged from 85 to 100%(6). It was determined to be safe in rats and pigs at doses as high as 3000 mg/m²/day (500 mg/kg/day) administered for 4 weeks and no significant clinical, hematology or chemistry abnormalities were noted.

In preclinical studies severity of toxoplasmosis was increased and activation of latent toxoplasmosis was noted in mice (unpublished data/7). Experimental colitis and encephalitis in preclinical studies were worsened by administration of 1-MT, although colitis and encephalitis have not been noted by administration of 1-MT alone. (8,9).

Seventeen patients with advanced/metastatic solid tumors having progressed on established salvage therapy have been studied in phase I clinical trial at dose escalating from 200 mg once daily to 600 mg twice daily continued till disease progression or 3 months with 3 patients treated

at each dose level. Pharmacokinetics for 1-MT has been linear within this dose range (7). This has been well tolerated in the patient groups so far and most patients had only grade I or II toxicities consistent with advanced disease in a heavily pretreated population (7). The most frequently reported adverse events (regardless of attribution), occurring in $\geq 30\%$ of patients, were fatigue, nausea and dyspnea (shortness of breath), muscle weakness (lower extremities), and pain in the lower extremities. The most frequently reported laboratory abnormalities (regardless of attribution), occurring in $\geq 30\%$ of patients, were lymphopenia, anemia, hypoalbuminemia, hyperglycemia, hypokalemia, and hyponatremia. In the higher dose cohorts two cases of mild hypophysitis were noted during therapy with D-1MT which resolved on its own without any pharmacologic intervention. The most frequently observed adverse event which is possibly related to D-1MT is muscle weakness of the lower extremities (25%). Lymphopenia (43.75%) is the most frequently observed laboratory abnormality possibly related to 1-MT. There have been two CTCAE grade 3 adverse events of hyponatremia and dizziness which were possibly related to 1-MT were reported.

In a separate phase I dose-escalation study, 48 patients have been treated to a maximal dose of 2000 mg bid without attaining a MTD (7). The pharmacokinetics on this study was very similar to the earlier phase I study except that AUC values did not show a proportional increase with dose at the highest dose. This is in line with experience in rats and dogs where plasma concentrations of drug plateau due to finite intestinal absorptive area. Based on pharmacokinetics of indoximod tested in phase I trial, a dose of 1200 mg bid has been proposed for the phase II trials. Twelve patients have been treated at this dose of 1200 mg bid or higher in the phase I clinical trial without any notable toxicity. Indoximod is currently being studied in an ongoing phase II clinical trial for patients with breast cancer at this dose of 1200 mg bid along with docetaxel.

When indoximod (1-MT) used immediately post sipuleucel-T as in this clinical trial, it might increase the side effects of cytokine release from last infusion of sipuleucel-T.

2.4 Rationale

It has long been established that the tumors cause local immune-suppression that leads to tolerance toward various tumor antigens. This is primarily mediated by a linked set of inhibitory mechanisms involving regulatory T cells (Tregs), which dominantly inhibit other T cells(5), and by inhibitory check-points including IDO, CTLA4 and PD-1. Vaccine therapy by itself is limited in its ability to overcome this anergy and immunosuppressive microenvironment, without somehow interrupting suppression by Tregs or one of the key inhibitory checkpoints.

The IDO pathway is an attractive target because it sits at a nexus between immunosuppressive checkpoint blockade and functional Treg inhibition. In Phase I trials, 1MT has had little toxicity (especially in patients who have not received prior immunotherapy). We hypothesize that inhibition of the IDO pathway by indoximod (1-MT) will permit a robust and possibly more sustained immune response to sipuleucel-T, which may lead to further improvement of anti-cancer effects. Importantly, preclinical mouse studies show that tumor-bearing hosts are primed to express high levels of IDO, and this host IDO actively suppresses anti-tumor T cell responses. Thus, indoximod when combined with sipuleucel-T would primarily target the IDO expressed by the host, which inhibits optimal anti-tumor T cell responses to sipuleucel-T. This means that it is not necessary or beneficial to screen patients for IDO expression in their tumors, or their sipuleucel-T preparation, because these are not the primary target of the therapy.

In this randomized double blind phase II trial, indoximod or placebo will be administered following standard of care sipuleucel-T therapy to assess the augmentation of immune response to sipuleucel-T. Indoximod /placebo will be self-administered orally twice daily starting after the last sipuleucel-T infusion on week 4 (with first leukapheresis being week 0) and will be continued for 6 months in the absence of disease progression.

We plan to offer trans-rectal biopsy of prostate prior to initiating therapy with sipuleucel-T and at 14 weeks from start of therapy for all patients who have an intact prostate and have not received radiation to the prostate. We will also offer biopsies to patients who have an easily accessible metastasis that can be biopsied before and after treatment. Biopsy of the primary tumor or metastatic site will help understand local immune response to treatment in individual patients. Simultaneous assessment of the immune response within the peripheral blood and within the tumor will help understand immune response to treatment and possibly establish markers of response. The information gained from this study would help devise strategies to better develop sipuleucel-T, indoximod and other immunotherapies for prostate cancer.

3 Patient Selection

Study entry is open to adult men regardless of race or ethnic background. While there will be every effort to seek out and include minority patients, the patient population is expected to be similar to that of other prostate cancer studies at the University Of Minnesota and other participating institutions.

Patients with metastatic castration resistant prostate cancer with minimally symptomatic or asymptomatic disease (the clinical indication for use of sipuleucel-t) will be considered for enrollment in this clinical trial.

Inclusion Criteria

- 3.1** Histologically documented adenocarcinoma of the prostate with metastatic disease as evidenced by soft tissue (e.g. lymphoid) and/or bony metastases on baseline CT scan of the abdomen and pelvis and/or bone scan
- 3.2** Castration-resistant based on a current or historical evidence of disease progression despite surgical or medical castration as demonstrated by one or more of the following:
 - PSA progression (defined as two consecutive PSA measurements at least 14 days apart ≥ 2.0 ng/ml and $\geq 50\%$ above the minimum PSA during castration therapy or above pre-treatment value if no response)
 - progression of measurable disease based on RECIST ($\geq 20\%$ increase in the sum of the diameters of all target lesions or the development of any new lesions – appendix III)
 - progression of non-measurable disease based on imaging studies pre section 9.4
- 3.3** Serum PSA ≥ 2.0 ng/ml at study enrollment
- 3.4** Castration levels of testosterone defined as ≤ 50 ng/dL at study enrollment

Must be at least 3 months from surgical castration or must have received medical castration therapy for at least 3 months and be receiving such therapy at the time of confirmed disease progression as defined in section 3.2
- 3.5** Asymptomatic or minimally symptomatic disease as demonstrated by ECOG Performance Status 0 or 1 (appendix II) and no need for opiate pain medications to control pain/symptoms
- 3.6** Age 18 years and older
- 3.7** Adequate bone marrow, renal and hepatic function within 14 days of study enrollment defined as:
 - Bone marrow: WBC $>3,000/$ mL or CD4 count >400 cells/mm³; platelets $>100,000/$ mL
 - Renal: creatinine <2.0 mg/dL OR creatinine clearance >60 mL/min/1.73 m²
 - Hepatic: total bilirubin <1.5 X institutional ULN; AST(SGOT) and ALT(SGPT) <2.5 X institutional ULN
- 3.8** Voluntary written consent

Exclusion Criteria

- 3.9** Visceral metastases (e.g. lung, liver, brain, kidney, spleen) as the safety and efficacy of sipuleucel-T has not been established in this patient population
- 3.10** Use of systemic corticosteroids or other immunosuppressive agents within the previous 4 weeks of study enrollment
- 3.11** HIV-positive patients and those with other acquired/inherited immunodeficiency
- 3.12** Active hepatitis including hepatitis B or C
- 3.13** History of gastrointestinal disease causing malabsorption or obstruction such as, but not limited to Crohn's disease, celiac sprue, tropical sprue, bacterial overgrowth/blind loop syndrome, gastric bypass surgery, strictures, adhesions, achalasia, bowel obstruction, or extensive small bowel resection
- 3.14** Inability to take medications by mouth
- 3.15** History of allergic reactions attributed to compounds of similar chemical or biologic composition of those used in this study
- 3.16** Active autoimmune disease, chronic inflammatory condition, conditions requiring concurrent use of any systemic immunosuppressants or steroids. Mild-intermittent asthma requiring only occasional beta-agonist inhaler use or mild localized eczema will not be excluded.
- 3.17** Previous allo-transplant of any kind
- 3.18** History of prior treatment with anti-CTLA4 blocking antibody

4 Patient Registration/Randomization

Registration will occur after the patient has signed the subject consent form and eligibility is confirmed, but before the 1st leukapheresis has been performed.

To be eligible for registration to this study, the patient must meet each criteria listed on the eligibility checklist (appendix I) based on the eligibility assessment documented in the patient's medical record. A copy of the eligibility checklist is also under attachments within the study in The Online Enterprise Research Management Environment (OnCore™).

4.1 Registration with Masonic Cancer Center Clinical Trials Office

Upon completion of the screening evaluation and obtaining written consent, the site study coordinator or designee will enroll the patient into OnCore. A copy of the signed consent and completed eligibility checklist must be uploaded as an attachment under the patient record in OnCore.

OnCore will notify key study personnel of the registration via a system generated email.

4.2 Patients Who Are Registered and Do Not Receive Sipuleucel-T

If a patient is registered to the study and is later found not able to begin sipuleucel-T, for whatever reason, he will be removed from study and treated at the physician's discretion. The patient will be considered a screen/baseline failure and the reason for removal from study will be clearly indicated in OnCore.

4.3 Patient Randomization

Each site will do their own randomization through the institutional investigational pharmacist using a randomized packet provided by the study statistician at the time of study site activation.

To be eligible for randomization a patient must have received all 3 doses of sipuleucel-T.

Patients will be randomized 1:1 to either indoximod or an identical looking placebo by notifying the institutional investigational pharmacist at the beginning of week 4 (the week of the 3rd leukapheresis/sipuleucel-T infusion).

Patients who are not randomized (ineligible or refuses) will be deemed unevaluable, removed from study and followed per standard of care, independent of this study.

Patients/research staff will not be un-blinded for the duration of the study except in the event of a medical emergency per section 7.5.

5 Treatment Plan

In order to provide optimal patient care and to account for individual medical conditions, the treating physician's discretion may be used in the prescribing of all supportive care drug therapy.

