6.2.1 Immune Monitoring Studies

At each time point in the previous table nine 10 cc green top tubes and one 10 cc red top tube will be collected. An additional serum sample (one 10 cc red top tube) will be collected at week 14.

All blood samples will be sent to Translational Therapy Laboratory (TTL) at University of Minnesota. Refer to the affiliate lab manual for the specimen specific shipping instructions.

T, NK, Treg by immunophenotype, NK cell function [CD107a and IFN production] measurements will be done in peripheral blood and tumor tissue at the Translational Therapy Laboratory (TTL) at University of Minnesota.

ELISPOT to PA2024, ELISA to measure antibody to PA2024 will be done at above specified time points from the peripheral blood by Dendreon.

Serum kynurenine, tryptophan, K/T ratio, and indoximod levels will be measured from peripheral blood at the specified time points by Newlink.

The pre and week 14 serum sample will be analyzed for immune biomarkers by Newlink.

If the patient consents at time of enrollment, aliquots of leftover serum will be stored from each blood draw at -80 degrees C in the Masonic Cancer Center's TTL for future testing. Permission to store leftover samples will be embedded in the treatment consent.

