11.2 Secondary Endpoints

- Antibodies to PA2024 as measured by ELISA
- Progression free survival
- Objective response rate as defined by Prostate Cancer Working Group -2 (PCWG2)(6)
- Overall survival and survival at two years
- Safety and tolerability
- Health related quality of life

12 Statistical Considerations

Our primary analysis will compare Tcell activation to PA2024 as measured by ELISPOT at 14 weeks between treatment groups using the two-sample t-test for unequal variance. This analysis will be completed on log-transformed data in the event that Tcell activation is skewed. A secondary analysis will be completed adjusting for any potential confounders or baseline differences using linear regression.(11)

Secondary endpoints CD54 count, antibodies to PA2024 and Tcell proliferation will be compared between groups in an unadjusted analysis using the two-sample t-test and an adjusted analysis using linear regression. Response rate will be summarized by group using contingency tables and the odds ratio for response will be estimated using logistic regression. Time to disease progression and overall survival will be summarized by Kaplan-Meier Curves and the hazard ratio estimated using Cox regression. In addition, quality of life will be measured by the FACT-P (a validated questionnaire consisting of four subscales of well-being: Physical, Social/Family, Emotional and Functional) and compared between treatment groups using the two-sample t-test for univariate analyses and multivariate linear regression for multivariate analysis.

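### Sites randomise separately, but the primary t-test leaves site out; this costs some efficiency, not validity, and is worth correcting if the site packets are blocked

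*Combined protocol and SAP*

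**What the plan says.** **Allocation.** Section 4.3: "Each site will do their own randomization through the institutional investigational pharmacist using a randomized packet provided by the study statistician". It adds: "Patients will be randomized 1:1 to either indoximod or an identical looking placebo". Packets are issued when a site is activated. Nothing says whether they are blocked. The synopsis gives the scale: "Approximately 50 subjects will be enrolled (1:1 indoximod vs placebo) at up to 5 sites".

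**Samples.** Under section 6.2.1 all blood goes to one university laboratory, and for transport it says: "Refer to the affiliate lab manual for the specimen specific shipping instructions". The same section has one company run every PA2024 ELISPOT.

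**Analysis.** Section 12 compares week-14 T-cell activation between arms "using the two-sample t-test for unequal variance". On scale it says: "This analysis will be completed on log-transformed data in the event that Tcell activation is skewed". A secondary linear regression adjusts for confounders or baseline differences that are not listed; site is not mentioned. Section 12.1 bases its 80% power on the same unadjusted comparison, on the log scale.

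**The concern.** Where allocation is made separately within sites, the usual analysis keeps site in the model. If each site's packet is balanced, differences between sites largely cancel out of the arm contrast. A t-test without site still counts those differences as noise when it estimates the standard error. The standard error is then too large, the test rejects too seldom under the null, and power is lost.

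Site differences are plausible here. ELISPOT measures interferon-gamma production by whole PBMC, and samples are drawn at different centres and travel different routes. Collection, transit and case mix can each differ by site. Variation between assay laboratories is not a candidate, because one company runs all the assays. Place of sipuleucel-T infusion is a weak argument for a site term: section 5.1 allows infusion by a referring physician, so it can vary within a site.

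At stake are a few points of power in a trial planned at 80%, and a choice about site that section 12 leaves open until data are in hand.

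**Working it through.** **1. The plan's own figure.** Inputs from section 12.1: coefficient of variation 1.6, 24 v 60 spots, 25 per arm, level 0.05 (sidedness is not stated; two-sided reproduces the figure).
- Log-scale SD = √ln(1 + 1.6²) = √1.270 = 1.127.
- Log-scale effect = ln(60/24) = ln 2.5 = 0.916.
- Noncentrality = 0.916 / (1.127 × √(2/25)) = 2.875.
- Power with 48 df = 0.804 (normal approximation 0.820). The stated 80% is reproduced.

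**2. Site in the model, arms balanced within site.** Let ρ be the share of log-ELISPOT variance due to site, lying inside the 1.6. The documents do not give ρ, so a range is assumed. The residual SD becomes 1.127 × √(1 − ρ), with 50 − 6 = 44 df for five sites. Power is 0.803 at ρ = 0, 0.822 at 5%, 0.842 at 10% and 0.882 at 20%.

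**3. Planned test against site model, packets blocked.** Simulation with 40,000 trials per cell, five sites (10 each, or 20/12/8/6/4; sizes assumed) and blocks of 4 within site:

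| Assumed site share | Power, planned t-test | Power, arm + site | Type-I error, planned |
|---|---|---|---|
| 5% | 0.81 | 0.82 | 0.047 |
| 10% | 0.82 | 0.84 | 0.043 |
| 20% | 0.84 | 0.88 | 0.035 |

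The site model holds 0.05 throughout. Independent repeats agree to about 0.01 in power. They put the planned test's type-I error at about 0.04 for a 10% share and, with blocks of 4, mostly at 0.035 to 0.038 for 20%. Splitting each site exactly in half gives slightly lower values at 20% (0.031 to 0.034).

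**4. Hand check of the conservatism.** Take five sites of 10, each split 5/5. The true variance of the arm difference is proportional to 1 − ρ. The expected within-arm sample variance is proportional to 1 − ρ(5 − 1)/(25 − 1) = 1 − ρ/6.
- ρ = 10%: ratio 0.900/0.983 = 0.915, square root 0.957. The critical value 2.011 acts like 2.011/0.957 = 2.10, a two-sided tail of about 0.041.
- ρ = 20%: ratio 0.800/0.967 = 0.828, square root 0.910. The critical value acts like 2.21, a tail of about 0.032.

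Both agree with the exact-halving simulation.

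**5. Packets not blocked.**
- A 10-man site splits 8–2 or worse with probability 2(1 + 10 + 45)/1024 = 0.109. At least one of five such sites does so with probability 1 − 0.891⁵ = 0.44.
- A 4-man site goes 4–0 with probability 2/16 = 0.125.
- The planned test keeps its level (0.045 to 0.052 in simulation).
- Adding site costs about 0.03 in power if sites do not differ (0.79 v 0.75 to 0.76), roughly breaks even at a 10% share (0.80 to 0.81 either way), and gains about 0.03 at 20% (0.82 v 0.85).

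**The case against.** The strongest reply is that nothing in the plan is invalid. With blocked packets the planned test is conservative and its simulated power, 0.81 to 0.84, is at or above the stated 80%. With unblocked packets its level stays near 5%. The gain depends on a site share that the documents never give, and at 5% it is one point. Block size is properly the statistician's business, and silence about it does not show that packets are unblocked. The secondary regression could already take site. A plain linear model would also drop the unequal-variance protection that section 12 chose. All of this stands. It limits the size of the point and makes the fix conditional, but it does not remove the mismatch between how men are allocated and how they are compared.

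Two stronger readings are tempting.

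- **Bias.** A reader might infer that lopsided sites mix handling differences into the treatment effect. Under randomisation such imbalance is chance variation, and the t-test's error rate already covers it.
- **An underpowered trial.** If site variation came on top of the 1.6, the planned test would fall to about 0.76 at a 10% share and 0.71 at 20% by formula (0.775 and 0.744 in simulation with balanced sites), against about 0.80 with site in the model. No section says that the 1.6 excludes site variation. If it came from multi-site data, it may already include it.

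Nor do the documents show that only affiliates' cells travel. The ELISPOT is run by an outside company, so the lead centre's material must leave the university too.

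**Conclusion.** The point holds as a matter of efficiency. The trial allocates by site, and the primary analysis ignores site. With blocked packets, and site variation inside the 1.6, the planned test gives up about 1, 2 and 4 points of power at assumed shares of 5%, 10% and 20%. Its type-I error falls to about 0.04 at 10% and 0.035 to 0.038 at 20%. The stated 80% is correct arithmetic and is still met. These figures rest on an assumed site share, five sites of assumed size, and blocks of 4. That site is missing from the analysis is certain; how much it matters is not. Whether a site model should be primary depends on a fact that the documents do not give, namely whether the packets are blocked.

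**What to change.** **Section 4.3.** State that site packets use permuted blocks within site. Packets are issued at activation and the protocol is at its sixth revision, so confirm this with the statistician for packets already issued, and use blocks for any new ones.

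**Section 12, if packets are blocked.** Make the primary comparison a linear model of log week-14 ELISPOT on arm plus site, pooling sites with fewer than 4 randomised men. Use heteroscedasticity-robust standard errors suited to small samples, to keep the unequal-variance protection. The HC2 form with Satterthwaite degrees of freedom is a natural choice, because without the site term its standard error is the Welch one. HC3 is conservative at this size and could give back the gain. The power figures above are for ordinary standard errors. Keep the Welch t-test as supporting.

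**Section 12, if packets already issued were not blocked.** Keep the t-test as primary and name site in the existing adjusted regression.

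**Cost.** A sentence or two in each section and no new data. The model uses up to 4 degrees of freedom. If sites do not differ, the loss under blocking is about 0.005 in power, or about 0.01 if 15% of week-14 samples are assumed missing. Unblocked, it would be about 0.03, which is why the change of primary analysis depends on blocking.
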